After randomization for this study was complete, an additional endpoint to assess Worst Skin Pain response was included in the sequential testing procedure. This additional endpoint is based on the threshold for clinically meaningful change and is defined as at least a 3 point decrease from Baseline in HSSDD weekly worst skin pain score at Week 16 among study participants with a score of ≥ 3 at Baseline. Note that the power calculations reported in Table 2-1 for this endpoint are based on the sample size that was initially driven by the Worst Pain CFB endpoint as described above. With a 2-sided significance level of 0.025, the sample size of 104:52 in the subset of participants reporting Baseline HSSDD worst skin pain score at or beyond the threshold for clinically meaningful change (ie, Baseline HSSDD ≥ 3) provides 53% power for

detecting a statistically significant difference between bimekizumab Q4W and placebo in the proportion of Worst Pain responders.

Note that the power at the 0.025 level of significance associated with this endpoint for the comparison between bimekizumab Q2W and placebo is 95%. The Q4W comparison of Worst Skin Pain response vs placebo against the 0.05 level of significance is therefore likely, and the power at this significance level is 65%. Given the strength of the power for the bimekizumab Q2W arm vs placebo across endpoints, it is considered acceptable to have a relatively low power for this final endpoint in the testing sequence for the bimekizumab Q4W treatment arm vs placebo.

Table 2-1: Power calculation assumptions and methods

Endpoint	Power $\alpha = 0.025$, 2-sided		Assumptions		
	Q2W	Q4W	Week 16 Bimekizumab Q2W N=280 ^a	Week 16 Bimekizumab Q4W N=140	Week 16 Placebo N=70
HiSCR ₅₀	0.99	0.90	Proportion responders=0.60	Proportion responders=0.50	Proportion responders=0.25
HiSCR ₇₅	0.99	0.98	Proportion responders=0.45	Proportion responders=0.35	Proportion responders=0.10
DLQI	0.99	0.96	Mean CFB=-5.4; SD=6.8	Mean CFB=-4.8; SD=6.8	Mean CFB=-0.8; SD=6.6
Worst Skin Pain CFB ^b	0.89	0.73	Mean CFB=-2.2; SD=3.2	Mean CFB=-2.0; SD=3.2	Mean CFB=-0.5; SD=3.7
Worst Skin Pain Response ^c	0.95	0.53	Proportion responders=0.53	Proportion responders=0.43	Proportion responders=0.23

CFB=change from Baseline; Q2W=every 2 weeks; Q4W=every 4 weeks; SD=standard deviation

Note: Estimates for HS0003 are based on Week 12 data from the HS0001 study.

^a Pooled Q2W at Week 16 from Q2W/Q2W and Q2W/Q4W arms

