^b Within-participant average of Worst Skin Pain according to 24-hour recall.

^c Assumes N=208, 104, 52 in Q2W, Q4W, and placebo, respectively, to account for Worst Skin Pain score at or above 3 (ie, the threshold for clinically meaningful change from Baseline).

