4 STATISTICAL/ANALYTICAL ISSUES

4.1 Adjustments for covariates

The primary efficacy analyses and selected secondary analyses will be adjusted for the 2 randomization stratification variables:

- Hurley Stage at Baseline (II or III)
- Baseline antibiotic use (Yes or No)

If a participant is stratified in the incorrect stratum (ie, the stratum recorded in the Interactive voice or web Response System differs from the actual stratum the participant belongs to), the actual stratum will be used for the analysis.

The continuous secondary endpoints will also include the Baseline value as a covariate.

The Worst Skin Pain secondary endpoints (change from Baseline continuous endpoint and pain response binary endpoint) will also include analgesic use as a covariate.

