Weekly averages will be derived for each of the items of the HSSDD for weeks matching the post-Baseline dosing weeks up to Week 16. A weekly average is the sum of the scored item over the course of the study week divided by the number of days on which the item was completed. The weekly averages will be relative to the respective visit date except for Baseline, which will be anchored to the first dose of study drug. A weekly average will only be calculated if at least 4 non-missing values (not necessarily consecutive) are available. Otherwise, the HSSDD weekly average for the given question will be set to missing.

Baseline will be computed as the average from the first 7 consecutive day period in which there are at least 4 non-missing entries. That is, first consider the first 7 consecutive days prior to the Baseline visit, but not including the Baseline visit day itself. If there are at least 4 non-missing values (not necessarily consecutive), then the Baseline average will be calculated. If there are less than 4 values, the 7 consecutive day period will move one day earlier. If there are at least 4 non-missing values (not necessarily consecutive) in that period, then the Baseline average will be calculated. This will continue until there are at least 4 non-missing values in a 7 consecutive day

period in the 14 days prior to Baseline. If there is no period in which there are at least 4 non-missing entries, then the Baseline value will be set to missing.

Change from Baseline in worst skin pain score is defined as the average Week 16 worst skin pain score minus the Baseline worst skin pain score. Missing data imputation described in Section 4.2.1.2 will be applied to the weekly averages and not to the individual daily PRO data.

8.3.3.1 Primary analysis of change from Baseline in skin pain score at Week 16

Change from Baseline in worst skin pain score will be presented by treatment group. The analysis model will be based on an ANCOVA with fixed effects of treatment, Hurley Stage at Baseline, Baseline antibiotic use, analgesic use (Section 6.4.2) and Baseline value as a covariate.

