The LSM, SE, and 95% CI for the LSM will be presented by treatment group. For the comparison between placebo and bimekizumab, the difference between the LSM, the associated 97.5% CI for the contrasts, and the corresponding p-value will be presented. If one dose regimen is tested at the 0.05 significance level as determined in Section 4.5, then the confidence interval will be 95% instead of 97.5% for that dose with a corresponding $Z_{\alpha/2}$ of 1.96.

8.3.3.2 Sensitivity analysis of change from Baseline in skin pain score at Week 16

A sensitivity analysis using the same analysis model as in Section 8.3.3.1 will be used, based on observed data. Estimand and intercurrent event details are specified in Table 8–2.

8.3.4 HSSDD skin pain response at Week 16

The analysis set for the analyses of the skin pain response will be restricted to those study participants in the RS with a Baseline worst skin pain score of 3 or higher. The weekly scores and Baseline score are derived as specified in Section 8.3.3.

8.3.4.1 Primary analysis of skin pain response at Week 16

Skin pain response at Week 16, as assessed by the “worst skin pain” item in the HSSDD, is defined as an improvement in the weekly worst skin pain score of at least 3 points versus Baseline.

The primary analysis will be based on a logistic regression model including a fixed effect for treatment, Hurley stage at Baseline, Baseline antibiotic use, and analgesic use (Section 6.4.2).

The odds ratio versus placebo, p-value (from Wald test), and 97.5% CI will be calculated. If one dose regimen is tested at the 0.05 significance level as determined in Section 4.5, then the confidence interval will be 95% instead of 97.5% for that dose. Missing data will be handled as specified in Section 4.2.1.2. Estimand and intercurrent event details are specified in Table 8–2.

The number and percentage of participants who are pain responders at Week 16 will be summarized by treatment group.

By-participant listings of pain response status will be provided.

8.3.4.2 Sensitivity analyses of Skin Pain Response at Week 16

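### The confirmatory model for skin pain response omits the Baseline pain score, which is on hand for everyone analysed and is used for the same score as a continuous outcome; the test is valid but gives up a little precision

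*SAP*

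**What the plan says.** Section 8.3.4.1 (SAP) specifies for the confirmatory pain response test a "logistic regression model including a fixed effect for treatment, Hurley stage at Baseline, Baseline antibiotic use, and analgesic use". Section 4.1 is consistent with that. It states "The continuous secondary endpoints will also include the Baseline value as a covariate", and for the dichotomy it adds only analgesic use ("pain response binary endpoint) will also include analgesic use as a covariate").

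The continuous form of the same weekly score is handled differently. The ANCOVA in Section 8.3.3.1 lists "Baseline antibiotic use, analgesic use (Section 6.4.2) and Baseline value as a covariate".

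The analysis set for pain response is "restricted to those study participants in the RS with a Baseline worst skin pain score of 3 or higher", so nobody can enter the analysis without a Baseline score. Section 4.2.2.1 also puts the Baseline value of the variable into the imputation model.

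On power, Section 2.4 and Table 2-1 give 53% for Q4W at two-sided 0.025, 65% at 0.05, and 95% for Q2W at 0.025. The sample sizes come from the Table 2-1 footnote: "Assumes N=208, 104, 52 in Q2W, Q4W, and placebo, respectively". For Q4W the SAP says "it is considered acceptable to have a relatively low power for this final endpoint in the testing sequence".

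**The concern.** Response is an absolute drop of 3 points on a score bounded at 0 and 10 (Table 4-2), with entry at 3 or more. A participant who starts at 3 responds only by averaging 0 at Week 16; one who starts at 9 responds by reaching 6. The endpoint definition itself therefore makes some dependence of response on Baseline likely. In a logistic model, leaving out a baseline predictor of the outcome costs power for the treatment effect.

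Two adjacent steps of the hierarchy thus analyse one score, and the Baseline value is used in only one of them, with no reason given. At stake is power for the Q4W pain response test, which has the lowest power in Table 2-1. To a smaller degree, the last step for either dose is affected, because under Section 4.5 success there passes alpha to the other dose.

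**Working it through.** **Inputs.** From Section 2.4 and Table 2-1: response rates 0.53 (Q2W), 0.43 (Q4W), 0.23 (placebo); n = 208, 104, 52; two-sided alpha 0.025 or 0.05; SD of change in worst skin pain 3.2 (both doses) and 3.7 (placebo). Assumed, because the SAP gives nothing: the Baseline distribution and the strength of its link to response.

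**1. The SAP's own power.** Arcsine approximation to Fisher's test: power = Φ(2·[asin√(p₂ − 1/(2n₂)) − asin√(p₁ + 1/(2n₁))] / √(1/n₁ + 1/n₂) − z).

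- Q4W, 0.025: asin√0.4252 = 0.7103; asin√0.2396 = 0.5115; 2 × 0.1988 / 0.1698 = 2.341; 2.341 − 2.241 = 0.099; power 0.540 (SAP 0.53).
- Q4W, 0.05: 2.341 − 1.960 = 0.381; power 0.648 (SAP 0.65).
- Q2W, 0.025: asin√0.5276 = 0.8130; 2 × 0.3015 / 0.1550 = 3.889; 3.889 − 2.241 = 1.648; power 0.950 (SAP 0.95).

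The stated figures reproduce.

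**2. Like-for-like starting point.** The planned test is a Wald test from logistic regression, not a Fisher-type test. The uncorrected two-proportion formula gives 0.588 for Q4W at 0.025, and simulated Wald tests without Baseline give 0.57 to 0.59. Gains must be read from about 0.58, not from 0.53.

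**3. Gain by assumed strength of Baseline.** Simulated Wald tests, 6,000 trials per setting, marginal response rates held at the SAP values, Q4W against placebo at 0.025:

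| Odds ratio per SD of Baseline | Without | With | Gain (points) |
|---|---|---|---|
| 1.0 | 0.589 | 0.585 | −0.4 |
| 1.25 | 0.586 | 0.585 | −0.1 |
| 1.5 | 0.574 | 0.593 | 1.9 |
| 2.0 | 0.586 | 0.629 | 4.3 |
| 2.5 | 0.585 | 0.656 | 7.1 |
| 3.0 | 0.580 | 0.688 | 10.8 |

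For Q2W at 0.025: 0.968 to 0.980 at an odds ratio of 2, and 0.965 to 0.987 at 3.

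**4. Which strength is plausible.** A bounded-score model was used: Baseline N(6, SD 2) truncated to 3-10; Week 16 = constant + slope × (Baseline − 6) + residual, limited to 0-10; constants chosen per arm to give the SAP response rates. Slopes were 0.3 to 0.7. The result depends on the residual SD σ, which the SDs of change can inform. Ignoring truncation and the scale limits, SD of change = √((1 − slope)² × 2² + σ²):

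- σ = 2: √(0.49 × 4 + 4) = 2.44 at slope 0.3; √(0.09 × 4 + 4) = 2.09 at slope 0.7. Both are well below 3.2.
- σ = 3: √(1.96 + 9) = 3.31 and √(0.36 + 9) = 3.06. These are near 3.2.

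Q4W gains at 0.025 were about 2 to 8 points with σ = 2 and about 0 to 3 with σ = 3. With σ set by arm to match 3.2 and 3.7 (4,000 trials per setting), power went from 0.574 to 0.592 (slope 0.3), 0.578 to 0.582 (0.5) and 0.596 to 0.601 (0.7). A further run of 3,000 trials per setting gave 0 to 8 points overall, 0 to 4 where the SD of change came near 3.2-3.7, and 0 to 2 for Q2W. Monte Carlo error on a single power figure is about √(0.58 × 0.42 / 3000) = 0.009, so runs can differ by a point.

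**5. Intercurrent events.** Under the composite strategy these count as nonresponse whatever the pain score, which weakens the link to Baseline. With an assumed 15% event rate at slope 0.3, the gain falls from 8.3 to 7.2 points (σ = 2) and from 5.9 to 4.5 (σ = 2.5).

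**6. Effect on the estimate.** The unadjusted Q4W odds ratio is (0.43/0.57)/(0.23/0.77) = 2.53. At an odds ratio per SD of 2, the value conditional on Baseline is 2.76. The estimand's number changes even though the effect does not.

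**The case against.** The SAP does not contradict itself. Section 4.1 sets one rule and Sections 8.3.3.1 and 8.3.4.1 follow it. The HiSCR models also omit Baseline lesion counts. The sponsor has accepted low Q4W power for this last test. Baseline pain is already used in the imputation model and in the ANCOVA one step earlier. The odds ratio is non-collapsible, and Section 8.2.2 defines it as conditional on the stratification factors, so a new covariate is not free of consequence; a continuous term also assumes linearity in the logit. All of this is correct, and it makes the point one of efficiency. It does not remove it. HiSCR is built on a percentage reduction, whereas pain response is a fixed drop on a bounded scale. Accepting low power from a given sample size is also not a reason to leave a collected predictor unused.

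Stronger readings are tempting and are not supported:

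- A reader might infer that Baseline pain largely determines response. The SAP has no figure for this.
- A reader might set simulated powers in the 0.60s against the stated 53%. That mixes two test formulas; the like-for-like start is about 0.58.
- A reader might call this the least-powered step for both doses. That holds for Q4W (0.53); for Q2W, pain change (0.89) is below pain response (0.95).
- A reader might conclude that the alpha-passing step is compromised. Q2W is the dose more likely to pass alpha, and it gains only about 0 to 2 points.

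**Conclusion.** The omission is real and worth correcting, as a matter of precision and consistency. The planned test is valid and type I error is not inflated. Adding Baseline pain would raise Q4W power at 0.025 by about 0 to 8 points over the assumed range, most plausibly 0 to 4, and Q2W power by about 0 to 2; no setting showed a material loss. These sizes rest on an assumed Baseline of N(6, SD 2) truncated to 3-10, assumed slopes of 0.3 to 0.7, and the Table 2-1 SDs of change, which come from Week 12 data of the earlier study and are not given for the subset with Baseline of 3 or more.

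**What to change.** Before unblinding, add the Baseline HSSDD worst skin pain score as a continuous covariate to the logistic model in Section 8.3.4.1. The sensitivity analyses in Section 8.3.4.2 inherit it. Amend Section 4.1 so that the Baseline value applies to the pain response endpoint as well as to the continuous secondary endpoints. State for this endpoint that the odds ratio is conditional on Baseline pain in addition to the covariates already listed.

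The cost is SAP wording and one model term; no new data are needed. Whether post-Baseline analgesic use should stay in the model is a separate question and not part of this change.

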8.3.4.2.1 Nonresponse imputation

As a sensitivity analysis, any missing data at Week 16 that are not preceded by an intercurrent event (Table 8–2) will be imputed as nonresponse. That is, participants who experience an intercurrent event will be imputed as nonresponder at the timepoint of the event and all subsequent timepoints (including any recorded data after the event), and all missing data will also be imputed as nonresponse.

The same analysis model as Section 8.3.4.1 will then be used on the imputed data set.

8.3.4.2.2 Analysis on observed cases

An additional supportive analysis will be based on observed data only for study participants with a worst skin pain score at Week 16 who have not had an intercurrent event on or before Week 16. Study participants with missing data or who have prematurely discontinued study treatment will be treated as missing (see Section 4.2.2).

The same analysis model as in Section 8.3.4.1 will then be used on the imputed data set.

8.4 Other efficacy endpoints

The other efficacy endpoints are listed below and will be evaluated according to the planned assessments in the protocol. This excludes the timepoints for the primary and secondary endpoints specified above in Section 8.2.1 and Section 8.3.

Missing data handling for these endpoints is described in Section 4.2.1.3.

8.4.1 HiSCR endpoints

8.4.1.1 HiSCR₂₅, HiSCR₅₀, HiSCR₇₅, HiSCR₉₀, and HiSCR₁₀₀

Categorical response variables HiSCR₂₅, HiSCR₅₀, HiSCR₇₅, HiSCR₉₀, and HiSCR₁₀₀ are defined to be equal to 1 if %ΔAN is less than or equal to -25%, -50%, -75%, -90%, and -100%, respectively, and the change from Baseline in the abscess count is zero or negative (ie, non-positive) together with a non-positive change from Baseline in the draining tunnel (fistula/sinus tract) count, and 0 otherwise. This definition is introduced for identifying study participants who respond to the treatment (1 = responder, 0 = nonresponder). The definition of percentage improvement from Baseline is given in Section 8.2.1.

HiSCR₂₅, HiSCR₅₀, HiSCR₇₅, HiSCR₉₀, and HiSCR₁₀₀ response will be summarized using frequency tables by treatment group and visit.

A line plot of the HiSCR responder (HiSCR₅₀, HiSCR₇₅, HiSCR₉₀, and HiSCR₁₀₀) rate over time, by treatment group, will be produced.

In order to investigate the effect of intercurrent event handling and missing data handling on the binary response variables, the following iterations of each of the aforementioned plots (HiSCR₅₀, HiSCR₇₅, HiSCR₉₀, and HiSCR₁₀₀, respectively) will be presented, with corresponding summary statistics tables:

- Observed data only (non-imputation for either intercurrent events or missing data)

- Non-response imputation to reflect intercurrent events, non-imputation for missing data
- Full imputation: non-response imputation to reflect intercurrent events, imputation for missing data per Section 4.2.1.3

Bar charts of HiSCR₅₀, HiSCR₇₅, HiSCR₉₀, and HiSCR₁₀₀ will be produced by visit and Hurley Stage at Baseline for the Initial Treatment Period and the combined Initial and Maintenance Treatment Period. These bar charts will be repeated for HiSCR by visit and Baseline antibiotic use.

Another bar chart of HiSCR rate at Week 16 will be produced by Hurley Stage at Baseline and Baseline antibiotic use.

In addition to the above bar charts, a stacked bar chart displaying whether the criteria are met (yes/no) for each of the component data used in the calculation of HiSCR (%ΔAN, abscess count and draining tunnel [fistula/sinus tract] count) will be generated by treatment group and visit. This graph will summarize the proportion of participants in each of the 8 different yes/no binary responses at each visit (2 x 2 x 2 response combination) at each visit.

8.4.1.2 Time to response of HiSCR₂₅, HiSCR₅₀, HiSCR₇₅, HiSCR₉₀, and HiSCR₁₀₀

See Section 8.4.1.1 for the derivation of HiSCR.

Initial Treatment Period

Time to HiSCR₂₅, HiSCR₅₀, HiSCR₇₅, HiSCR₉₀, and HiSCR₁₀₀ (in days) during the Initial Treatment Period will each be calculated as:

Min (Date of first HiSCR_{xx} response, Date of Week 16 visit) – Date of first dose of study medication + 1, here xx represents 25, 50, 75, 90, 100 respectively. All visits including unscheduled visits are considered.

Participants who discontinue study treatment without achieving a given HiSCR response prior to Week 16 visit will be censored at the date of last lesion count assessment. Participants who reach the Week 16 Visit without achieving the given response will be censored at the date of the Week 16 Visit. Participants who experience an intercurrent event prior to achieving a HiSCR response will be censored at the date of the intercurrent event. Participants will be censored at Baseline if there is no Baseline lesion count assessment or no Post-Baseline lesion count assessment.

Time to HiSCR₂₅, HiSCR₅₀, HiSCR₇₅, HiSCR₉₀, and HiSCR₁₀₀ response during Initial Treatment Period will each be estimated and presented using the Kaplan-Meier product-limit method for each treatment group.

Kaplan-Meier plots of time to HiSCR responses will be presented by treatment group. In these Kaplan-Meier plots, the line will start at 0 (since there are no responders at Week 0) and will increase over time, representing time to achieving the response.

The median time to response, including the 2-sided 95% confidence interval, will be calculated for each treatment. Comparisons of bimekizumab vs placebo will be analyzed using a log-rank test stratified by Hurley Stage at Baseline and Baseline antibiotic use.

Combined Initial and Maintenance Treatment Period

An additional time to HiSCR_{25} , HiSCR_{50} , HiSCR_{75} , HiSCR_{90} , and HiSCR_{100} (in days) during the combined Initial and Maintenance Treatment Period will be calculated as above, where the Week 48 visit is considered instead of Week 16.

Time to HiSCR_{25} , HiSCR_{50} , HiSCR_{75} , HiSCR_{90} , and HiSCR_{100} response during the combined Initial and Maintenance Treatment Period will each be estimated and presented using the Kaplan-Meier product-limit method for each treatment group.

Kaplan-Meier plots of time to HiSCR responses will be presented by treatment group. In these Kaplan-Meier plots, the line will start at 0 (since there are no responders at Week 0) and will increase over time, representing time to achieving the response.

The median time to response, including the 2-sided 95% confidence interval, will be calculated for each treatment.

8.4.1.3 HiSCR_{25} , HiSCR_{50} , HiSCR_{75} , HiSCR_{90} , and HiSCR_{100} response at both Weeks 16 and 48

See Section 8.4.1.1 for the derivation of HiSCR response.

The number and percentage of HiSCR_{25} , HiSCR_{50} , HiSCR_{75} , HiSCR_{90} , and HiSCR_{100} responders at both Weeks 16 and 48 will be summarized based on the RS and MS.

Missing data for the above summaries will be handled using NRI. That is, participants are counted as responders only if they have an observed HiSCR at both Weeks 16 and 48 and have no intercurrent events through Week 48. Otherwise, they are treated as not responding.

